1. SYNOPSIS

Name of Sponsor/Company: Vanda Pharmaceuticals Inc.

Name of Investigational Product: iloperidone

Name of Active Ingredient: iloperidone, VYV-683

Title of Study: A multicenter, randomized, double-blind, placebo-controlled study to evaluate the efficacy and safety of iloperidone for 4 weeks in the treatment of patients with acute manic episodes associated with Bipolar I Disorder

Study center(s): Approximately 50 sites across the U.S. and Europe

Studied period (years):

Phase of development:

Estimated date first patient enrolled: March 2021

Phase III

Estimated date last patient completed (through the Short-Term

Treatment Phase): May 2022

Number of patients (planned): 400 (200 iloperidone and 200 placebo)

Diagnosis and main criteria for inclusion:

- Meet the *Diagnostic and Statistical Manual of Mental Disorder, Fifth Edition* (DSM-5) diagnosis of bipolar I disorder, manic or mixed type, as confirmed by the Structured Clinical Interview for Diagnostic and Statistical Manual of Mental Disorders, Fifth Edition (SCID) manic or mixed type with or without psychotic symptoms
- Men and women between the ages of 18-65 years inclusive
- Had at least one prior documented manic or mixed episode (with or without psychotic symptoms) that required treatment prior to screening
- Patients with Young Mania Rating Scale (YMRS) total score ≥ 20
- Patients with ≥ 4 on at least 2 of 4 YMRS items (irritability, speech, content, disruptive/aggressive behavior)
- Patients with Montgomery-Asberg Depression Rating Scale (MADRS) total score < 18
- Voluntarily hospitalized for current manic episode

Main Exclusion Criteria:

- Patients with a DSM-5 diagnosis other than bipolar I disorder that was the primary focus of treatment within the previous six months
- Patients experiencing a first manic episode or meeting criteria for rapid cycling

Investigational product, dosage and mode of administration:

Iloperidone will be provided as overencapsulated tablets containing either 1, 3, 6, 9, or 12 mg.

Duration of treatment:

Short Term Double-Blind Treatment Phase (4 weeks)

Titration Period – 1 week

Double-Blind Treatment Period – 3 weeks

Optional Open-Label Extension Phase (52 weeks)

Open-label Titration Period – 1 week

Open-label Extension Period – 51 weeks

Reference therapy, dosage and mode of administration:

Placebo will be provided in size and appearance that are visually identical to those containing iloperidone.

Primary Objective:

To evaluate the efficacy of iloperidone monotherapy compared to placebo in the treatment of adult patients with bipolar I disorder experiencing an acute manic or mixed episode as measured by reduction in the Young Mania Rating Scale (YMRS) total score at Week 4

Secondary Objective(s):

- To evaluate the efficacy of iloperidone monotherapy compared to placebo in the treatment of adult patients diagnosed with bipolar I disorder experiencing an acute manic or mixed episode as measured by improvements in the Clinical Global Impression of Severity (CGI-S)
- To evaluate the efficacy of iloperidone monotherapy compared to placebo in the treatment of adult patients diagnosed with bipolar I disorder experiencing an acute manic or mixed episode as measured by reduction in the Young Mania Rating Scale (YMRS) total score at each trial visit
- To assess the rate of YMRS responders. A YMRS responder is defined as at least a 50% decrease from baseline in YMRS total score
- To assess the efficacy of iloperidone monotherapy compared to placebo in improving clinical symptomatology in adult patients diagnosed with bipolar disorder, manic or mixed episodes after acute treatment as measured by CGI-C
- To assess the efficacy of iloperidone monotherapy compared to placebo in improving clinical symptomatology in adult patients diagnosed with bipolar disorder, manic or mixed episodes after acute treatment as measured by MADRS
- To assess the safety and tolerability of iloperidone compared to placebo in the treatment of adult patients in an acute manic or mixed episode of bipolar I disorder as measured by changes in vital signs and weight, laboratory analytes, electrocardiograms (ECGs), and the incidence and severity of TEAEs and extrapyramidal symptoms (EPS) using the Barnes Akathisia Scale, Simpson-Angus Scale, and the AIMS

Exploratory Objective:

• To conduct a whole genome association scan to identify potential markers of response and safety for a bipolar indication

Open-label Extension (OLE) Objective:

• To explore the long-term safety and tolerability of dosing with iloperidone over an additional 52 weeks of treatment

Overall Design: This will be a multicenter, randomized, double-blind, placebo-controlled, parallel-group study. The study has two phases: the Pre-Randomization Phase and the Short-Term Treatment Phase and is followed by an optional third phase, the Open-Label Extension (OLE) Phase. The Pre-Randomization Phase includes the Screening visit and the Baseline visit. The Short-Term Treatment Phase includes two periods: (1) the Titration Period and (2) the Double-Blind Treatment Period. The optional OLE Phase also includes two periods: (1) the OLE Titration Period and (2) the OLE Maintenance Period.

The Pre-Randomization Phase begins with the screening visit (Day -7 to -1) during which an informed consent will be obtained from potential patients and their eligibility will be initially assessed. The Screening Visit (Day -7 to -1) and Baseline Visit (Day 0) will be separated by a maximum of 1 week. Patients meeting all entry criteria for enrollment into the study will enter the Short-Term Treatment Phase. During this Phase, patients will undergo a 7-day Titration Period where iloperidone or placebo will be titrated to 24 mg/day total daily dose given as a bid regimen (12 mg bid) utilizing a fixed titration regiment, whereby the doses will be increased to $2\rightarrow 6\rightarrow 12\rightarrow 18\rightarrow 24\rightarrow 24\rightarrow 24$ mg/day (bid doses of 1, 3, 6, 9, 12, 12, and 12 mg). The target dose for CYP2D6 poor metabolizers is 12mg/d (6 mg bid) utilizing a fixed titration regiment, whereby the doses will be increased to $2\rightarrow 6\rightarrow 12\rightarrow 12\rightarrow 12\rightarrow 12\rightarrow 12\rightarrow 12$ mg/day (bid doses of 1, 3, 6, 6, 6, 6, and 6 mg). Patients will discontinue current antipsychotic treatment prior to the first day of the Titration Period (Day 1-7). Patients will remain in-patient during this period to ensure compliance with dosing.

Subjects continuing to meet the criteria for randomization will be eligible to proceed to the Double-Blind Treatment Period. During this period, patients will be randomized 1:1 to either iloperidone or placebo, stratified by country. Subjects will remain in this period for up to 3 weeks.

Subjects who complete the Double-Blind Treatment Period will be eligible to participate in the optional OLE Phase. Eligible subjects will enter the 7-day OLE Titration Period where iloperidone will be titrated to 24 mg/day total daily dose given as a bid regimen (12 mg bid). The target dose for CYP2D6 poor metabolizers is 12mg/d (6 mg bid). Subjects will then enter the OLE Maintenance Period in which subjects will be treated with iloperidone for up to 52 weeks.

Criteria for evaluation:

Mean baseline-to-endpoint change in total score using following parameters:

Efficacy:

- Young Mania Rating Scale (YMRS)
- Overall and mania severity of illness for Clinical Global Impression of Severity (CGI-S)
- Clinical Global Impression of Change (CGI-C)
- Montgomery-Asberg Depression Rating Scale (MADRS)

Safety:

- Adverse Events (AEs) and proportion of patients withdrawing due to AEs
- EPS scale scores as measured by Simpson-Angus Scale (SAS), Abnormal Involuntary Movement Scale (AIMS), and Barnes Akathisia Rating Scale (BARS)
- Metabolic risk factors, clinical chemistry, hematology, vital signs, and weight
- Columbia Suicide-Severity Rating Scale (C-SSRS)
- CYP2D6 genotyping
- 12-lead electrocardiograms (ECG)

Statistical methods:

If not otherwise specified, statistical significance is defined as $p \le 0.05$ and is two-tailed when appropriate. Data base lock will occur after 4-week ST double-blind period. The primary efficacy variable is the change from baseline in the YMRS total score.

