11.2.4. Demography and Other Baseline Data

Demographic data and patient characteristics at screening/baseline will be listed and summarized by treatment group for all randomized patients using descriptive statistics.

Past and current medical history will be summarized by treatment group using the system organ class (SOC) as coded using the Medical Dictionary for Regulatory Activities (MedDRA) coding dictionary.

Past medical conditions will be defined as an onset date prior to randomization (Visit 2) and resolved (not on-going) as of Visit 2. Current medical conditions, defined as an onset date on or after the date of randomization (Visit 2) or an onset date prior to randomization (Visit 2) and unresolved (on-going) as of Visit 2, will be reported separately, but similarly to the past medical conditions. If both a past and a current (on-going) medical condition record are indicated for a condition, the condition will be presented under current medical conditions only.

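### The eligibility check placed after the treated titration week conflicts with randomization at Visit 2 and, if a site re-applies the YMRS threshold there, Week 4 data are lost because of early improvement

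*Combined protocol and SAP*

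**What the plan says.** The Synopsis, Overall Design, contains two accounts of when patients qualify and are allocated.

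**After titration.** Following the description of the 7-day Titration Period it says "Subjects continuing to meet the criteria for randomization will be eligible to proceed to the Double-Blind Treatment Period". The next sentence, referring to the Double-Blind Treatment Period, is "During this period, patients will be randomized 1:1 to either iloperidone or placebo, stratified by country".

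**Before titration.** The same section says "The Pre-Randomization Phase includes the Screening visit and the Baseline visit", and titration lies outside that phase. It says "Patients meeting all entry criteria for enrollment into the study will enter the Short-Term Treatment Phase", and that phase begins with titration. In titration itself, "patients will undergo a 7-day Titration Period where iloperidone or placebo will be titrated to 24 mg/day total daily dose", so an arm has already been assigned. Section 11.2.4 places randomization at Visit 2 ("Past medical conditions will be defined as an onset date prior to randomization (Visit 2"), and section 11.2.6 places the first dose at Visit 2 as well.

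The criteria for randomization are not set out separately. The Synopsis lists main inclusion criteria, among them "Patients with Young Mania Rating Scale (YMRS) total score ≥ 20" and a score of at least 4 on two of four named YMRS items. The primary objective is "reduction in the Young Mania Rating Scale (YMRS) total score at Week 4".

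**The concern.** The wording describes a second eligibility check after a week of blinded treatment, and the only listed criteria include thresholds on the primary outcome scale. A site that takes the sentence at face value and rates a patient at 28 on entry and 17 after titration could conclude that the patient may not proceed. Selection would then depend on response to treatment. If the drug works in week 1, it removes more iloperidone than placebo patients.

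The consequence depends on which account of randomization is right:

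- **Randomization after titration.** Patients who improved below the threshold are never randomized.
- **Randomization at Visit 2.** They are randomized and dosed. Section 11.2.2 keeps them in the Intent-to-Treat population if they have an on-treatment post-baseline efficacy rating, and the MMRM of section 11.3.1 can use that rating. Their Week 4 scores are still lost because of their outcome. The MMRM is then protected only under missing at random, and only if a YMRS from the end of titration exists and is in the model.

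The plan does not say how patients who do not proceed are followed or analysed. With about 50 sites, the sentence may also be applied differently from one site to another.

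**Working it through.** **1. The plan's own power (section 11.1).** Inputs: 200 per arm, difference 3.6, SD 11, two-sided 0.05. SE = 11 × √(2/200) = 1.10. Power = Φ(3.6/1.10 − 1.96) = Φ(1.313) = 0.905; the noncentral t gives 0.904. The stated figure of around 90% is reproduced, so the sample-size arithmetic is correct.

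**2. Illustration of a YMRS ≥ 20 check at Day 7.** The difference of 3.6 and SD of 11 at Week 4 come from section 11.1. Everything else is assumed: baseline YMRS normal with mean 28 and SD 5, truncated at 20; Day 7 change with SD 8; Day 7 to Week 4 correlation 0.6; and three sets of mean Day 7 change. A YMRS rating at the end of titration is also assumed, because the visit schedule is not in the public text.

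- Share failing = P(baseline + Day 7 change < 20), by arm.
- Proceeders-only difference = difference between arms in mean Week 4 change, given a Day 7 score of at least 20.
- Common-slope estimate: among proceeders, regress Week 4 change on arm, Day 7 change and baseline; then add (Day 7 slope) × (baseline-adjusted Day 7 arm difference in all 400).
- Power = Φ(estimate/SE − 1.96), with 200 per arm entering titration.

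| Mean Day 7 change, placebo / iloperidone | Below 20, placebo / iloperidone | Difference, proceeders only | Power, proceeders only | Power, common slope, all Day 7 data |
|---|---|---|---|---|
| −4 / −5 | 31% / 35% | 3.3 | about 75% | about 81% |
| −6 / −7.5 | 39% / 46% | 3.0 | about 63% | about 75% |
| −8 / −10 | 48% / 56% | 2.8 | about 47% | about 70% |

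The common-slope estimate itself stays near 3.6, because the simulated loss is missing at random given the Day 7 score.

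*Hand check, proceeders only.* In the simulation, selection narrows the Week 4 SD to about 10.2 (first row) and 10.0 (last row).

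- First row: n = 200 × 0.69 = 138 and 200 × 0.65 = 130. SE = 10.2 × √(1/138 + 1/130) = 1.247. Φ(3.3/1.247 − 1.96) = Φ(0.69) = 0.75.
- Last row: n = 104 and 88. SE = 10.0 × √(1/104 + 1/88) = 1.448. Φ(2.8/1.448 − 1.96) = Φ(−0.03) = 0.49. The lower end is therefore best read as just under one half.

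*Hand check, common slope.* The simulated SEs are about 1.265 and 1.46. Φ(3.6/1.265 − 1.96) = Φ(0.89) = 0.81, and Φ(3.6/1.46 − 1.96) = Φ(0.51) = 0.69, or 0.70 with unrounded inputs.

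**3. Responders (at least a 50% fall from baseline), middle row.** With assumed mean Week 4 changes of −10.4 and −14.0 (3.6 apart), about 36% on placebo and 49% on iloperidone respond when everyone is followed. Among proceeders the rates are about 21% and 30%. If the last available value is used instead, which is how section 11.2.1 defines endpoint, stopped patients count by their Day 7 score:

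- Placebo: 0.61 × 20.5% + 0.39 × 40.7% = about 28%.
- Iloperidone: 0.54 × 29.9% + 0.46 × 45.3% = about 37%.

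The difference between arms falls from about 13 points to about 9 either way.

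**4. Sensitivity.** A milder set assumes baseline mean 26-32, mean Day 7 placebo change −4 with SD 7, and correlation 0.5-0.7. The check then removes 17-36% on placebo and 17-44% on iloperidone. With a Day 7 drug effect of 1.0-1.8 points, the proceeders-only difference is about 2.8-3.4 and power 59-83%. With no Day 7 drug effect the difference stays at about 3.6.

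**5. If the 400 are counted after the check.** Power for a difference of 3.6 stays near 90%, but 400/(1 − q) patients must start titration: 445, 500 or 572 for failure fractions q of 10%, 20% or 30%.

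**The case against.** The strongest reply is that the check is inferred. No text says that YMRS ≥ 20 is re-applied, or even rated, at Day 7. The Synopsis gives only main criteria, and the eligibility section and visit schedule are not in the public text. Eligibility is first assessed at Screening, so a requirement to go on meeting the criteria for randomization fits the Screening-to-Baseline step. The randomization sentence that follows looks displaced in the same way. This is a good argument, and it is why the point is framed as a conflict to be reconciled. It does not make the printed order harmless: a site reads the sentence where it stands, and nothing in the text rules out the literal reading.

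Three stronger readings are tempting, and the documents do not support them.

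- A reader might infer that the Week 4 comparison is made in early non-responders. With randomization at Visit 2, stopped patients with a post-baseline rating remain in the Intent-to-Treat population and the MMRM. The threshold is also an absolute score: a patient going from 40 to 20 has improved by half and still passes.
- A reader might quote power as low as 64-34%. That range needs a separate Week 4 regression in each arm, which the plan does not specify.
- A reader might say the responder analysis has no way to include stopped patients. The endpoint definition in section 11.2.1 could bring in their last score, although this still lowers the rates and narrows the difference.

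**Conclusion.** The point holds as an internal contradiction with a material consequence if the sentence is applied as printed. The Synopsis places a check on the criteria for randomization after treated titration, against its own phase definitions and against Visit 2 in sections 11.2.4 and 11.2.6. If the YMRS criteria are re-applied there, patients are stopped because of their outcome. With randomization at Visit 2, the harm is outcome-dependent loss of Week 4 data, which the MMRM covers only under missing at random with an end-of-titration YMRS in the model. With randomization after titration, the trial population itself changes.

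In the illustration, power falls from about 90% to about 81-70% (common slope, all Day 7 data) or about 75-47% (proceeders only) when the 200 per arm are counted before the check. All of these figures rest on assumed Day 7 means, SDs and correlation and on an assumed Day 7 rating. They show plausible size and are not a forecast. Re-application of the threshold is itself an inference.

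**What to change.** Reconcile the Overall Design text with sections 11.2.4 and 11.2.6. Move the sentence on the criteria for randomization, and the randomization sentence after it, to the Screening-to-Baseline step. State the randomization visit and define the criteria. Make clear that the YMRS severity criteria for randomization are assessed before the first dose and are not an outcome-based condition for staying in the Week 4 comparison.

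State also that randomized patients who do not proceed past titration, for any reason, still have YMRS rated at the scheduled visits through Week 4 and are included in the primary and responder analyses. This concerns data collection and analysis only. It does not say who should continue treatment, and it leaves untouched any safety or other re-check elsewhere in the protocol.

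The cost is a few sentences in the Synopsis, matching text in the protocol body, and follow-up ratings for patients who stop early. It should be settled before enrolment, because Week 4 scores that were never taken cannot be recovered.

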11. STATISTICAL PLAN

11.1. Sample Size and Accrual

Based on a two-sided t-test with the 5% significant level, the planned sample size of 200 subjects per arm (a total of 400 subjects) provides around 90% power to detect a mean difference of 3.6 in YMRS (change from baseline at week 4) assuming a standard deviation of 11 in each treatment group.

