11.2.1. General

Statistical analyses will be performed using two-sided tests at alpha level of 0.05.

Data will be summarized by treatment group (and by visit when applicable), with respect to demographic and baseline characteristics, efficacy variables, and safety variables.

Summary statistics will include the mean, N, standard deviation, median, minimum, and maximum values for continuous variables, and frequencies and percentages for categorical variables.

For the analyses of change from baseline, only patients with a baseline and at least one post-baseline measure will be included in the analysis. Unless otherwise specified, baseline is defined as the latest non-missing observation across all the visits in the screening phase, before the active study drug begins. Endpoint will be the latest non-missing observation across all the post-baseline visits in the treatment phase.

Low enrolling sites will be pooled for analysis and the pooling algorithm will be determined prior to breaking the blind. The goal of pooling low enrolling sites is to have a sufficient number of patients per treatment group within a site for the analysis models. Unless otherwise specified, the pooled sites will only be used in the analyses where the site has an effect. The actual sites rather than the pooled sites will be specified in the data listings.

Details of the model and the analyses will be specified in the SAP. All statistical analyses will be performed using SAS®, Version 9.1.3 or higher.

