11.2.2. Patient Populations for Analysis

The following analysis populations will be defined for this study:

Intent-to-Treat: will include any patient randomized into the study that receives a dose of study drug and that has completed at least one post-baseline efficacy measurement while on study medication;

Safety: Any patient randomized into the study that receives a dose of study drug;

Per-Protocol: Any patient who is randomized and receives the protocol required study drug exposure and required protocol processing.

Efficacy analyses will be performed on the Intent-to-Treat population and the Per-Protocol population. Safety summaries will be based on Safety set. Patient characteristics will be presented for all patients randomized.

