11.2.3. Patient Disposition

Study completion and reasons for discontinuation for all randomized patients in the treatment phase will be summarized for each treatment group. Discontinuations by reason will be tabulated for each treatment group.

As needed, time to discontinuation due to adverse events, lack of efficacy and for any reason may be analyzed using Kaplan-Meier survival techniques; the log-rank test may be used for group comparison.

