11.3. Efficacy Data Analysis

11.3.1. Primary Outcome

The primary efficacy outcome measure is the change from baseline in the Young Mania Rating Scale (YMRS) total score at Week 4. The primary statistical method will be mixed effect model repeat measurement (MMRM). A detailed description of the primary analysis model, and other supportive analyses will be included in the SAP.

As stated previously, any changes in the statistical methods that occur prior to database lock will be documented in the SAP and will not require a protocol amendment.

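### Does Section 11.1 overstate power by attaching around 90% to the full planned 200 per arm, with no allowance for missing Week 4 YMRS?

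*Combined protocol and SAP*

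**What the plan says.** Section 11.1 opens its calculation with "Based on a two-sided t-test with the 5% significant level" and states that "the planned sample size of 200 subjects per arm (a total of 400 subjects) provides around 90% power". The inputs are a difference of 3.6 YMRS points in change from baseline at Week 4 and a standard deviation of 11 in each arm. The synopsis has the same total: "Number of patients (planned): 400 (200 iloperidone and 200 placebo".

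Section 11.1 does not say whether 200 counts patients randomized or patients with a Week 4 score, and it mentions no attrition. Other places provide for losses without giving a rate:

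- The synopsis lists among its safety criteria "Adverse Events (AEs) and proportion of patients withdrawing due to AEs".
- Section 11.2.3: "Discontinuations by reason will be tabulated for each treatment group".
- Section 11.2.1, on change from baseline: "only patients with a baseline and at least one post-baseline measure will be included in the analysis".
- Section 11.2.2 limits the Intent-to-Treat set to randomized, dosed patients with a record "that has completed at least one post-baseline efficacy measurement while on study medication".

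On the primary analysis, Section 11.3.1 says "The primary statistical method will be mixed effect model repeat measurement (MMRM"), with the model detail left to the SAP.

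**The concern.** The number behind the power figure is the whole planned enrolment, so the calculation appears to assume that every patient entered has a Week 4 score. A trial in acute mania with an active arm and a placebo arm will lose some patients, and the plan itself arranges to tabulate withdrawals. The Intent-to-Treat definition admits a patient on one post-baseline score, so belonging to that set does not guarantee Week 4 data. The power is also computed for a t-test although the primary analysis is a repeated-measures model.

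The margin above 90% is two patients per arm. If losses were large, a reader who took 90% at face value would overrate what a null result shows.

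**Working it through.** **Inputs.** From Section 11.1: difference 3.6, SD 11 per arm, two-sided alpha 0.05, n = 200 per arm. From the synopsis: 1:1 allocation, 400 planned. No dropout rate is given, so every rate below is an assumption.

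**Step 1: reproduce the plan's figure.** For a two-sample t-test the noncentrality is δ = 3.6 / (11 × √(2/n)), on 2n − 2 degrees of freedom. At n = 200, δ = 3.6 / (11 × 0.1) = 3.273 on 398 df. The noncentral t distribution gives power 90.4%; the normal approximation gives 90.5%. The stated figure is right.

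**Step 2: margin above 90%.** Power is 90.1% at 198 per arm and 89.98% at 197. So 198 is the smallest number giving at least 90%, and the slack is 2 of 200, or 1%.

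**Step 3: how power falls if only patients with Week 4 data count.** With n = 200 × (1 − loss):

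| Assumed loss | n per arm | Power | Difference detectable with 90% power |
|---|---|---|---|
| 0% | 200 | 90.4% | 3.57 |
| 5% | 190 | 88.9% | 3.67 |
| 10% | 180 | 87.2% | 3.77 |
| 20% | 160 | 83.1% | 4.00 |
| 30% | 140 | 77.9% | 4.28 |

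Read the other way, power reaches 89% at 4.7% loss, 88% at 7.8%, 85% at 15.7% and 80% at 26.2%.

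**Step 4: the planned method.** The repeated-measures model keeps the earlier scores of patients who leave, so Step 3 is pessimistic. The assumptions here are four weekly visits, a quarter of the dropout before each visit (the first quarter therefore contributes nothing), AR(1) or compound-symmetry correlation, and within-patient correlation 0.5 to 0.8. Summing the information over dropout patterns gives an effective n per arm for the Week 4 contrast, which goes into the Step 1 formula:

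| Assumed loss | Effective n per arm | Power |
|---|---|---|
| 5% | 190.8–195.2 | 89.0–89.7% |
| 10% | 181.6–190.2 | 87.5–88.9% |
| 20% | 163.0–179.9 | 83.8–87.2% |
| 30% | 144.4–168.9 | 79.1–85.0% |

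**Step 5: what baseline adjustment would need to supply.** The documents do not say whether the model adjusts for baseline YMRS. If it does, the residual variance falls. The exact requirement for 90% is 197.2 per arm, so the fractional reduction that restores 90% is 1 − (effective n / 197.2):

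- 5% loss: about 1–3%
- 10% loss: 1 − 190.2/197.2 = 0.035 to 1 − 181.6/197.2 = 0.079, about 4–8%
- 20% loss: about 9–17%
- 30% loss: about 14–27%

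The square root converts this to a correlation between baseline and change: about 0.19 to 0.28 at 10% loss, and 0.30 to 0.42 at 20%.

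**The case for a change.** The best argument for acting is that the sentence leaves its reader unable to tell whether 90%, 87% or 83% applies. Every scenario in Step 4 falls below 90%, so the repeated-measures model recovers only part of the loss. Patients with no post-baseline score add nothing under any method. Baseline adjustment may make up the difference, but the plan does not state it. The general rule in Section 11.2.1, which takes the last available observation as endpoint, does not help either, because Sections 11.1 and 11.3.1 both fix the primary outcome at Week 4. The sections that defer detail to the SAP concern methods, not sample size. One added sentence would cost almost nothing.

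Most of that is true, and the omission stands: Section 11.1 does not say what the 200 counts or what missingness is expected. It does not follow that the stated power is wrong. The two-patient margin matters only against a claim of at least 90%, and the plan says around 90%. A loss of 5% leaves that wording plainly fair, and 10% arguably so. The passages on withdrawals are routine reporting and do not show that a loss near 20% was expected. Nor is the reader stranded: Section 11.1 gives the difference, SD, alpha, test and n, from which power at any loss can be computed, as above. A null result would in any case be read mainly from the estimate and its confidence interval, which already reflect the data actually obtained.

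**Conclusion.** The concern does not call for a change. The power statement is arithmetically correct at 90.4%, and its approximate wording tolerates modest loss of Week 4 data. It would become clearly too favourable only with losses of about 20% or more and no offset from baseline adjustment; nothing in the synopsis or Section 11 establishes either condition.

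What remains is a reporting gap of a familiar kind. The natural reading is that 200 per arm are to be randomized, that the t-test serves as a simple planning stand-in for the repeated-measures model, and that dropout and any covariate gain pull in opposite directions. Spelling this out would be a courtesy to the reader. It would leave the 400 patients, the conduct, the analysis and the result as they are.

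This conclusion rests on the synopsis and Section 11 only. The loss rates, visit schedule, dropout pattern and correlations in Steps 3 to 5 are assumptions, not figures from the plan.
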